8 RESEARCH QUESTION AND OBJECTIVES

8.1 PRIMARY OBJECTIVE

The primary objective of this study is to assess the effectiveness of the Praluent (brand name of alirocumab) dosing recommendations for the 3 dosage regimens approved to date, ie, 75 mg once every two weeks, 150 mg once every two weeks, and 300 mg once every 4 weeks (monthly) to avoid very low LDL-C levels.

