9.3.3 Prescriptions of Praluent

- 1. Date of initial prescription,
- 2. Dose and dosing frequency,
- 3. Number of doses prescribed,
- 4. Number of renewals, date(s) of renewal(s), and dosage and dosing frequency at renewals,
- 5. Reason for any Praluent dosage regimen modification.

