9.3.4 Discontinuation of Praluent, if relevant

- 1. Date of discontinuation;
- 2. Reason for discontinuation:
 - (1) Description of reason, if available.
 - (2) Unspecified.

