9.7.1 Primary analysis

Descriptive analyses will be conducted for each wave separately. In addition, analyses will be conducted using the entire data of all 3 waves.

Point estimates of proportions and 95% confidence intervals will be calculated.

Data will be summarized using mean, first quartile, median, third quartile, standard deviation and range for continuous parameters and counts, percentages and 95% confidence intervals if needed for categorical parameters. The analyses will be performed, overall, by countries, and for specific analyses (starting dose of Praluent, occurrence of very low LDL-C level) will also be presented based on baseline LDL-C levels.

The following descriptive analyses will be presented on the eligible population:

A. Occurrence of very low LDL-C level

An LDL-C level <25 mg/dL (0.65 mmol/L) is defined as very low; and an alternative definition with a cut-off at 15 mg/dL (0.39 mmol/L) will also be used.

For each definition of very low LDL-C level, the following statistics will be calculated:

- 1. The proportion of patients who have at least 1 very low LDL-C level during the 6-month observational period:
 - (1) In the whole analysis population,
 - (2) According to baseline LDL-C level (<70; 70 to <100; 100 to <130; 130 to <160; 160 to <190; ≥190 mg/dL),
 - (3) According to Praluent starting dose.
- 2. All occurrences of very low LDL-C levels will be classified according to the Praluent regimen received at the time of the corresponding LDL-C test.

B. Evolution of LDL-C level after the occurrence of very low LDL-C level

- 1. Among the patients who have a LDL-C level of <25 mg/dL (0.65 mmol/L) at any dose, the proportions of patients whose LDL-C level returns to ≥25 mg/dL (0.65 mmol/L) within 8 weeks after the lab test, if data available, and at any time until the end of the 6-month observational period after index date, respectively.
 - (1) Overall,
 - (2) By the action of dosage regimen modification or discontinuation of Praluent, or change in dosing frequency of Praluent, or lowering doses of other lipid-lowering drugs, or discontinuation of other lipid-lowering drugs.
- 2. Same analysis will be conducted for the patients who have LDL-C level <15 mg/dL (0.39 mmol/L).

C. Change in treatment after the occurrence of very low LDL-C level

For each definition of very low LDL-C level, the following statistics will be calculated:

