Among the patients who have a very low LDL-C level at a specific dosage regimen, within 8 weeks after the lab test and at any time until the end of the 6-month observational period after index date, respectively:

- (1) The proportion of patients for whom the dose of Praluent is changed to another dose regimen,
- (2) The proportion of patients for whom Praluent is discontinued,
- (3) The proportion of patients for whom the dosing frequency of Praluent is changed at least once,
- (4) The proportion of patients for whom the doses of other lipid-lowering drugs are decreased at least once,
- (5) The proportion of patients for whom other lipid-lowering drugs are discontinued,
- (6) The proportion of patients for whom no change in Praluent treatment or dose and/or other lipid-lowering drugs have been made.

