9.7.2 Secondary analysis

A. The starting dose of Praluent

- 1. The proportion of patients for whom Praluent is started at 75 mg Q2W, 150 mg Q2W, or 300 mg Q4W:
 - (1) In the whole analysis population;
 - (2) According to baseline LDL-C level:
 - a) <70 mg/dL (<1.81 mmol/L),
 - b) 70 to < 100 mg/dL (2.59 mmol/L),
 - c) 100 to < 130 mg/dL (3.37 mmol/L),
 - d) 130 to < 160 mg/dL (4.14 mmol/L),
 - e) 160 to < 190 mg/dL (4.92 mmol/L),
 - f) $\geq 190 \text{ mg/dL } (4.92 \text{ mmol/L}).$
 - (3) According to diagnosis of heterozygous familial hypercholesterolemia, ASCVD, diabetes and chronic kidney disease.
- 2. Mean baseline LDL-C level by starting dose.

B. Modification of the dosage regimen of Praluent

- 1. The proportion of patients for whom the dosage regimen of Praluent is modified during the 6-month observational period.
 - An estimate of the event rate at the end of the 6 months by a Kaplan-Meier approach.
- 2. Among the patients for whom the dosage regimen of Praluent is modified from the initial dose during the 6-month observational period:
 - (1) The median time to dosage regimen modification estimated using time-to-event approach (Kaplan Meier methodology),
 - (2) The mean LDL-C levels prior to and at least 4 weeks after the dosage regimen modification respectively,
 - (3) The proportion of patients for whom the dosage regimen is adjusted back to the initial regimen.

C. Timing of LDL-C tests

- 1. The mean time from the first prescription of Praluent to a LDL-C test in patients having a LDL-C test after initiation of Praluent and the median time estimated using a Kaplan-Meier approach in all patients having a follow-up,
- 2. The mean time from a dosage regimen modification to a LDL-C test in patients having a LDL-C test after initiation of Praluent and the median time estimated using a Kaplan-Meier approach in all patients having a follow-up.

D. Discontinuation of Praluent

- 1. Proportion of patients for whom Praluent is discontinued during the 6-month observational period after index date:
 - (1) Overall,
 - (2) By starting dose.
- 2. Among the patients for whom Praluent is discontinued:
 - (1) Proportion of patients on each dose regimen (75 mg Q2W versus 150 mg Q2W versus 300 mg Q4W) prior to discontinuation,
 - (2) Proportions of patients who had LDL-C <25 mg/dL (0.65 mmol/L) and <15 mg/dL (0.39 mmol/L) prior to discontinuation, respectively,
 - (3) Proportion of patients according to each reason for discontinuation, if available,

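### Primary analysis C counts Praluent changes after a very low LDL-C by timing alone and leaves the recorded reasons unused, so it cannot separate responses to the low value from changes made for other causes

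*Protocol*

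**What the plan says.** Protocol Section 8.1 sets the aim: "The primary objective of this study is to assess the effectiveness of the Praluent (brand name of alirocumab) dosing recommendations for the 3 dosage regimens" in avoiding very low LDL-C. Section 9.7.1 lists three primary descriptive analyses: A (occurrence), B (later LDL-C course) and C, headed "Change in treatment after the occurrence of very low LDL-C level".

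Part C takes patients with a very low value on a given regimen and reports six proportions, each over two windows: "within 8 weeks after the lab test and at any time until the end of the 6-month observational period after index date". C(1) is a change of regimen, C(2) is "The proportion of patients for whom Praluent is discontinued", and C(3) is a change of dosing frequency. C(4) and C(5) are reductions and stops of other lipid-lowering drugs, and C(6) is no change. B.1(2) groups the return of LDL-C to 25 mg/dL or above in part "By the action of dosage regimen modification or discontinuation of Praluent". None of these items refers to a reason.

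Reasons are nevertheless among the variables. Section 9.3.3, item 5 is "Reason for any Praluent dosage regimen modification". Section 9.3.4 has "Reason for discontinuation", recorded as a description where available and otherwise as unspecified. Only the second reappears in the analysis section, as secondary item D.2(3) of Section 9.7.2: "Proportion of patients according to each reason for discontinuation, if available".

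**The concern.** Part C is the primary analysis that shows most directly what physicians do once a very low LDL-C is on file, and it sits under an effectiveness objective. A patient with a very low value at week 6 who stops at week 20 for an unrelated cause enters C(2) exactly as does one whose physician stopped because of the result. C(1) and C(3) go further: an increase and a decrease count alike. The same patients also leave C(6), so the share with no action is understated if C is read as a record of response.

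The window running to month 6 is the more exposed of the two, because it leaves more time for unrelated changes. The information needed to separate the cases is already collected, but no planned table brings it together with the very low value.

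**Working it through.** **1. Items in C against the variables collected**

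| Item in 9.7.1 | Reason collected? | Where the reason is analysed | Crossed with a very low LDL-C? |
|---|---|---|---|
| C(1) regimen change | Yes, 9.3.3 item 5 | Nowhere in 9.7 | No |
| C(2) discontinuation | Yes, 9.3.4, if available | 9.7.2 D.2(3), all discontinuers | No |
| C(3) frequency change | Yes, under 9.3.3 item 5 if recorded as a regimen modification | Nowhere in 9.7 | No |
| C(4), C(5) other lipid-lowering drugs | No; 9.3.5 has name, date, dose and frequency | Not possible | No |

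Section 9.7.2 D.2(2) reports a very low LDL-C before discontinuation, but as a line separate from the reasons in D.2(3). Section 9.7.2 F.2 and Section 11 report adverse events tied to a change or stop of Praluent, again without reference to C.

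**2. The protocol's own figures (Section 9.5.1)**

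- Wave 1 rate: 3/61 = 4.9%, as stated.
- Totals: 68 + 251 + 135 = 454 and 68 + 251 + 255 = 574, as stated.
- Exact (Clopper-Pearson) 95% intervals at 5%: 3.19 to 7.43 for N = 454 and 3.37 to 7.11 for N = 574. These agree with the printed 3.2 to 7.4 and 3.4 to 7.1.

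No figure in the protocol is in dispute.

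**3. How many patients part C rests on**

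- 5% of all enrolled: 0.05 × 454 = 22.7; 0.05 × 574 = 28.7.
- The 4.9% was observed among patients with a follow-up LDL-C (61 of 68). If that share holds throughout: 22.7 × 61/68 = 20.4; 28.7 × 61/68 = 25.7.

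This gives about 20 to 29 patients over all waves, before the split by regimen. Wave 1 alone has three.

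**4. Weight of one unrelated change**

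- 1/29 = 3.4 points and 1/20 = 5.0 points in the pooled analysis.
- 1/3 = 33 points in the Wave 1 analysis.

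**5. Illustration (counts assumed, not from the protocol)**

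Suppose 5 of 23 patients stop: 5/23 = 21.7% (exact 95% CI 7.5 to 43.7). Of the five, let one have low LDL-C as the recorded reason, two another stated reason and two none.

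- Stops recorded as due to low LDL-C: 1/23 = 4.3%.
- Upper bound, adding the unspecified: (1 + 2)/23 = 13.0%.
- What C(2) would show: 21.7%.

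With other assumed splits, the share due to the low value can lie anywhere from 0% to 21.7%. The protocol gives no rate of unrelated changes that would narrow this.

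**The case against.** The strongest reply is that the protocol claims nothing causal. The analyses are called descriptive, the headings of B and C say only that something came after, and no combined proportion of patients acted upon is defined. That is correct. A reader might infer that the plan treats every later change as an answer to the result, but the text does not say so. What stands is narrower: under an effectiveness objective, C is where a reader looks for a response, and it cannot show one.

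A reader might also infer that stops for adverse events are hidden. They are not: F.2, D.2(3) and Section 11 report them. They are simply not linked to patients with a very low value. The 8-week window limits dilution but does not identify cause. Analysis A, which bears most directly on avoiding very low LDL-C, is unaffected.

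It can further be said that this is detail for the SAP, which is not shown and may add the breakdown. Section 9.7, however, is offered as the specification for the SAP and lists its tables item by item, including one by reason in D.2(3). It specifies C without one.

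Finally, reasons may be missing, the protocol defines no reason categories, and splitting 20 to 29 patients leaves very small cells. These points stand and shape the fix.

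**Conclusion.** The point holds for C(1) to C(3) and the Praluent actions in B.1(2). These are primary results counted by timing alone, while a reason that would separate responses from other changes is collected and not used with them. If C is read as physicians' response, changes for other causes can only raise C(1) to C(3) above the number of true responses and lower C(6).

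The size is known only per patient: about 3 to 5 percentage points for each unrelated change in the pooled analysis. This assumes a 5% rate of very low LDL-C, 454 to 574 patients, and follow-up LDL-C in between 61/68 and all of them. A total inflation of, say, 10 to 20 points should not be claimed, since it would only return an assumed rate of unrelated changes. Nor does the point extend to every treatment change, because for C(4) and C(5) there is no collected reason to use. It is worth correcting before the final analysis, but it does not undermine the study.

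**What to change.** - In 9.7.1 C(1) to C(3), and for the Praluent actions in B.1(2), report each proportion by recorded reason: low LDL-C, other stated reason, unspecified. Give low LDL-C as the count of responses, and low LDL-C plus unspecified as its upper bound. Keep the all-cause proportion beside them.
- Report C(1) and C(3) also by direction of change, with a stated analysis convention for switches between regimens with the same four-week total (2 × 150 mg = 300 mg).
- Where cells are very small, as in single waves or by regimen, use a patient listing showing the very low value, the change, its timing and its reason.
- Tabulate the reasons from 9.3.3 item 5 in 9.7.2 B, as D.2(3) does for discontinuation.
- State in Section 9.9 that no reason is collected for changes in other lipid-lowering drugs, so C(4) and C(5) remain temporal only.

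Cost: protocol or SAP wording, table shells and a short coding rule for recorded reasons. No new variable is needed, and the final report can apply the split to all three waves. The price is small cells, and a range instead of one figure where the reason is unspecified.

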9.7.2 Secondary analysis

A. The starting dose of Praluent

- 1. The proportion of patients for whom Praluent is started at 75 mg Q2W, 150 mg Q2W, or 300 mg Q4W:
 - (1) In the whole analysis population;
 - (2) According to baseline LDL-C level:
 - a) <70 mg/dL (<1.81 mmol/L),
 - b) 70 to < 100 mg/dL (2.59 mmol/L),
 - c) 100 to < 130 mg/dL (3.37 mmol/L),
 - d) 130 to < 160 mg/dL (4.14 mmol/L),
 - e) 160 to < 190 mg/dL (4.92 mmol/L),
 - f) $\geq 190 \text{ mg/dL } (4.92 \text{ mmol/L}).$
 - (3) According to diagnosis of heterozygous familial hypercholesterolemia, ASCVD, diabetes and chronic kidney disease.
- 2. Mean baseline LDL-C level by starting dose.

B. Modification of the dosage regimen of Praluent

- 1. The proportion of patients for whom the dosage regimen of Praluent is modified during the 6-month observational period.
 - An estimate of the event rate at the end of the 6 months by a Kaplan-Meier approach.
- 2. Among the patients for whom the dosage regimen of Praluent is modified from the initial dose during the 6-month observational period:
 - (1) The median time to dosage regimen modification estimated using time-to-event approach (Kaplan Meier methodology),
 - (2) The mean LDL-C levels prior to and at least 4 weeks after the dosage regimen modification respectively,
 - (3) The proportion of patients for whom the dosage regimen is adjusted back to the initial regimen.

C. Timing of LDL-C tests

- 1. The mean time from the first prescription of Praluent to a LDL-C test in patients having a LDL-C test after initiation of Praluent and the median time estimated using a Kaplan-Meier approach in all patients having a follow-up,
- 2. The mean time from a dosage regimen modification to a LDL-C test in patients having a LDL-C test after initiation of Praluent and the median time estimated using a Kaplan-Meier approach in all patients having a follow-up.

D. Discontinuation of Praluent

- 1. Proportion of patients for whom Praluent is discontinued during the 6-month observational period after index date:
 - (1) Overall,
 - (2) By starting dose.
- 2. Among the patients for whom Praluent is discontinued:
 - (1) Proportion of patients on each dose regimen (75 mg Q2W versus 150 mg Q2W versus 300 mg Q4W) prior to discontinuation,
 - (2) Proportions of patients who had LDL-C <25 mg/dL (0.65 mmol/L) and <15 mg/dL (0.39 mmol/L) prior to discontinuation, respectively,
 - (3) Proportion of patients according to each reason for discontinuation, if available,
 - (4) Proportion of patients who restart Praluent in the 6-month observational period.

E. Reason for Praluent prescription

Proportion of patients with LDC-C levels ≥70 mg/dL with statins +/- other lipid lowering therapies and having at least one criterion of a high or very high cardiovascular risk.

F. Adverse events

Number and proportion of patients with AE during the observational period will be presented:

- 1. Overall.
- 2. AEs that are co-reported with a subsequent change in the Praluent administration (ie, it is written in the medical chart that the Praluent administration is changed due to the AE, please refer to Section 11 for AE details).

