"The usual starting dose for Praluent is 75 mg administered subcutaneously once every 2 weeks. Patients requiring larger LDL-C reduction (>60%) may be started on 150 mg once every 2 weeks, or 300 mg once every 4 weeks (monthly), administered subcutaneously.

The dose of Praluent can be individualised based on patient characteristics such as baseline LDL-C level, goal of therapy, and response. Lipid levels can be assessed 4 to 8 weeks after treatment initiation or titration, and dose adjusted accordingly (up-titration or down-titration). If additional LDL-C reduction is needed in patients treated with 75 mg once every 2 weeks or 300 mg once every 4 weeks (monthly), the dosage may be adjusted to the maximum dosage of 150 mg once every 2 weeks."

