9.2.1 Duration of the study

The study will be conducted in 3 waves during 3 consecutive years.

The rationale for conducting the 3 waves when treatment patterns are evaluated across 3 different cohorts of Praluent prescribers and their patients is as follows:

- To confirm the effectiveness of the SmPC dosing recommendations risk minimization measures observed in the repeated waves.
- To observe the trend in practice over time, if any, by comparing findings across the 3 waves.
- Using 3 waves will also allow getting preliminary data available sooner, with the earliest availability at the end of the first wave.

After the first Praluent prescription identified during the eligibility period (Mar to Jun 2017 for Wave 1, Jul 2017 to Jun 2018 for Wave 2, and Jul 2018 to Jun 2019 for Wave 3), the observation period will last 6 months for each patient: from their first prescription to 6 months later, at the latest until the end of December 2017, 2018 and 2019, respectively.

After the end of the 6-month observation period, submission of appropriate documentation to Regulatory Authorities (if applicable according to local regulations) and/or Ethics Committees will be performed, in parallel, the physicians will be enrolled and informed of the main purpose of the study and upon all relevant approvals are obtained, the patients will be selected up to the first quarter (Q1) of 2019, 2020, and 2021 following the observation period, respectively.

The data will be collected retrospectively from the second quarter (Q2) 2018 to Q1 2019 in Wave 1, from Q1 2019 to Q1 2020 in Wave 2 and from Q1 2020 to Q1 2021 in Wave 3, respectively. Please see details in Figure 1 and Figure 2.

Figure 1 - Annual study progress in Wave 1

Wave 1

[figure not shown]
[figure not shown]

Figure 2 - Annual study progress in Waves 2 and 3

Waves 2 and 3

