9.3.6 LDL-C values

The most recent value prior to or on the index date (baseline) and all values in the observational period:

- 1. Date of the test.
- 2. Value of LDL-C.

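### The before-and-after LDL-C summary for regimen changes (9.7.2 B.2(2)) is two unpaired means whose later window does not close at a further change or stop, so it can misstate the LDL-C change on the modified regimen

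*Protocol*

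**What the plan says.** Protocol Section 9.7.2, part B.2, defines one group: "Among the patients for whom the dosage regimen of Praluent is modified from the initial dose during the 6-month observational period". For that group, item (2) specifies "The mean LDL-C levels prior to and at least 4 weeks after the dosage regimen modification respectively", and item (3) specifies "The proportion of patients for whom the dosage regimen is adjusted back to the initial regimen". Part D.1 of the same section reports the "Proportion of patients for whom Praluent is discontinued during the 6-month observational period after index date", and D.2(4) counts patients who restart.

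The LDL-C data available for item (2) are set by Section 9.3.6: "The most recent value prior to or on the index date (baseline) and all values in the observational period". Section 9.2.1 states that "the observation period will last 6 months for each patient: from their first prescription to 6 months later".

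The label text reproduced in Section 7.1 covers titration in both directions: "Lipid levels can be assessed 4 to 8 weeks after treatment initiation or titration, and dose adjusted accordingly (up-titration or down-titration").

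**The concern.** A reader who sees a mean LDL-C before a regimen change beside a mean LDL-C after it will take the gap as what happened to LDL-C on the modified regimen. The wording of B.2(2) does not secure that reading, for two reasons.

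- **Which later values count.** The rule has a lower limit of 4 weeks and no rule tied to treatment. A value taken after the patient has gone back to the initial regimen, or is off Praluent, meets the wording as long as it falls at least 4 weeks after the modification.
- **Which patients contribute.** Nothing requires a patient to have both values. Some modified patients will be in the prior mean only.

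At stake is the interpretability of the one planned summary of LDL-C around regimen modification. That summary supports the secondary objective of describing use against the dosing recommendations.

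**Working it through.** The protocol gives no expected value, precision or test for this item, so there is no stated figure to reproduce. The check sets the sections side by side and then illustrates size on assumptions.

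**1. Comparison within the protocol.**
- Section 9.7.1 B and C give comparable follow-up windows explicit upper limits: 8 weeks, and the end of the 6 months.
- Section 9.7.1 A.2 ties each very low value to the regimen in force when the test was done.
- Section 9.7.2 B.2(2) states no upper limit and no link to the regimen at the time of the test. Its only outer bound is the end of data collection (9.2.1, 9.3.6).
- Reversal (B.2(3)), discontinuation (D.1) and restart (D.2(4)) are all expected in the same 6 months.

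**2. Length of the later window.** Taking 6 months as about 26 weeks, a modification at week m leaves max(0, 26 − (m + 4)) weeks:

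| Modified at week | 4 | 8 | 12 | 16 | 20 | 22 or later |
|---|---|---|---|---|---|---|
| Weeks left | 18 | 14 | 10 | 6 | 2 | 0 |

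If modifications were spread evenly over weeks 4 to 26 (assumption), (26 − 22)/(26 − 4) = 4/22 = 18% could never have a later value. If the retest came only at 8 weeks, the share is (26 − 18)/22 = 8/22 = 36%. Testing also follows routine care: Section 9.5.1 reports that 61 Wave 1 patients had any LDL-C value during observation, and 68 were enrolled, so 7/68 = 10% had none.

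**3. Later values off the modified regimen.** Let r be the share of later values taken after a reversal or a stop. All LDL-C levels here are assumed.
- *Upward modification*: prior 100, on modified regimen 70, true change −30. After a full reversal the level is 100 and the apparent change is −30(1 − r). After a stop, with an assumed level of 130, it is −30 + 60r.
- *Downward modification*: prior 70, on modified regimen 100, true change +30. After a full reversal it is +30(1 − r). After a stop at 130 it is 30 + 30r.

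| r | Up, reversal | Up, stop | Down, reversal | Down, stop |
|---|---|---|---|---|
| 10% | −27 | −24 | +27 | +33 |
| 20% | −24 | −18 | +24 | +36 |
| 30% | −21 | −12 | +21 | +39 |

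Reversals shrink the difference. Stops shrink it after an upward change (the sign turns once r exceeds 30/60 = 50% on these levels) and enlarge it after a downward one.

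**4. Unequal subsets.** Assume half the patients have prior 80 and half prior 120 (mean 100), with a true change of −30 in each.
- If 50% of the lower and 90% of the higher group are retested, the later mean is (0.25 × 50 + 0.45 × 90)/0.70 = 75.7, so the difference is −24.3.
- With the shares swapped, it is (0.45 × 50 + 0.25 × 90)/0.70 = 64.3, so the difference is −35.7.
- With everyone retested, it is −30.

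**5. Mixed directions.** B.2(2) does not separate upward from downward modifications. With assumed changes of −30 and +30, an upward share of 50%, 70% or 90% gives a pooled change of 0, −12 or −24.

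**The case against.** The strongest reply is that this is detail for the SAP. Section 9.7 describes itself as specifications for that document, and the SAP is not at hand. Which value counts, whether values are paired and how later changes are handled are commonly settled there. This has weight, but the protocol is not silent: it fixes a summary (two means) and one side of a window. An SAP that follows it literally inherits the problem.

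A second reply is that B.2(2) defines no difference and no test, and that describing LDL-C before and after a change, whatever happens next, is legitimate. That is fair for a utilization study, and limiting values to those before a further change does select on later behaviour. But the table would then need to say that it does not describe LDL-C on the modified regimen.

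Third, some context is reported elsewhere: reversals in B.2(3), stops and restarts in D, and time from modification to an LDL-C test in C.2. This helps, but it does not show which values entered the later mean.

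Stronger readings that a reader might infer are not supported:
- **That the window is open-ended.** LDL-C collection ends with the 6-month observational period.
- **That the plan prescribes a comparison of different patients.** B.2 names one group for both means; different subsets are possible, not required.
- **That the bias always runs towards zero.** This is true of reversals, but not of stops, as the working shows.

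**Conclusion.** The point holds as a weakness in how one descriptive secondary summary is specified. As written, B.2(2) can mix in values taken off the modified regimen and can set a prior mean beside a later mean from a different subset of patients.

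The size cannot be derived from the protocol. The even spread of modification times, the LDL-C levels, the shares of reversals and stops, and the retest rates are all assumptions. On them, a true change of 30 mg/dL is shown as 27 to 21 when 10% to 30% of later values follow a full reversal, and unequal retesting moves it to between about 24 and 36. The cut-off near week 22 follows from the 4-week rule and about 26 weeks of observation.

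A reader should not carry this over to the primary objective: the proportions with very low LDL-C in Section 9.7.1 do not use this summary. It is worth correcting, but it is not critical.

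**What to change.** Replace B.2(2) with the paired within-patient change in LDL-C, reported separately for upward and downward modifications, in patients who have both:

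- the last LDL-C value before the modification; and
- the first LDL-C value at least 4 weeks after it and before any further regimen change or discontinuation of Praluent.

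Alongside it, give the number of modified patients without such a pair and the time from modification to the test used.

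**Cost.** No new data are needed: prescription and renewal dates with regimen (9.3.3), discontinuation date (9.3.4) and LDL-C test dates and values (9.3.6) are already collected. Patients without both values drop out of this one summary, and their number would be shown. The Wave 1 interim report was due in Q3 2019, before this July 2020 amendment, and the Wave 2 report is due in Q3 2020. The Wave 1 and Wave 2 tables for this item would therefore need re-running in the final report to keep the waves comparable. The primary analysis does not change.

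### Praluent regimen changes are analysed without direction, so before/after LDL-C means mix opposite movements and a counted change after a very low value need not be a reduction

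*Protocol*

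**What the plan says.** The label text quoted in section 7.1 has lipid levels checked after initiation or titration and the "dose adjusted accordingly (up-titration or down-titration"). It also describes moving from 75 mg Q2W or 300 mg Q4W to 150 mg Q2W, named as the maximum, when more LDL-C reduction is needed.

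Section 9.7.2 B (secondary) does not use that distinction:
- B.1 is "The proportion of patients for whom the dosage regimen of Praluent is modified during the 6-month observational period", with a Kaplan-Meier estimate at 6 months.
- B.2 is set in one group: "Among the patients for whom the dosage regimen of Praluent is modified from the initial dose during the 6-month observational period".
- B.2(2) asks for "The mean LDL-C levels prior to and at least 4 weeks after the dosage regimen modification respectively".

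Section 9.7.1 (primary) covers what follows a very low value:
- B.1(2) reports return to at least 25 mg/dL by action taken, among patients very low at any dose. Praluent modification and frequency change have no direction; for other lipid-lowering drugs the action is a lowering.
- C is set "Among the patients who have a very low LDL-C level at a specific dosage regimen, within 8 weeks after the lab test" and also to the end of the 6 months.
- C(1) is "The proportion of patients for whom the dose of Praluent is changed to another dose regimen".
- C(3) is "The proportion of patients for whom the dosing frequency of Praluent is changed at least once".
- C(4) is "The proportion of patients for whom the doses of other lipid-lowering drugs are decreased at least once".

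Section 9.3.3 collects dose and frequency at each renewal and the reason for any regimen modification.

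**The concern.** The study asks whether the dosing recommendations avoid very low LDL-C. For that, the direction of a change carries most of the information. Lowering the dose after a very low value and raising it after an inadequate response are different events, with opposite expected effects on LDL-C.

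If they are pooled in 9.7.2 B, neither the modification rate nor the before/after means can be read as describing either kind of titration. If direction is also missing from 9.7.1 B.1(2) and C, a change listed as following a very low value may be read as a protective response when it was an increase or left the 4-weekly dose unchanged. C(4) shows that the protocol states direction where it means a reduction, and section 11 likewise refers to dose decrease when sorting adverse events. The omission for Praluent is therefore inconsistent with the protocol's own practice.

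**Working it through.** The protocol gives no figure for the number, direction or LDL-C effect of modifications, so there is none to reproduce. The check is of the text, plus three short calculations.

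**1. What a modification can be.** Dose per 4 weeks is 2 x 75 = 150 mg for 75 mg Q2W, 2 x 150 = 300 mg for 150 mg Q2W, and 1 x 300 = 300 mg for 300 mg Q4W.

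| From | To | Change in mg per 4 weeks |
|---|---|---|
| 75 mg Q2W | 150 mg Q2W | +150 |
| 75 mg Q2W | 300 mg Q4W | +150 |
| 150 mg Q2W | 75 mg Q2W | -150 |
| 150 mg Q2W | 300 mg Q4W | 0 |
| 300 mg Q4W | 75 mg Q2W | -150 |
| 300 mg Q4W | 150 mg Q2W | 0 (label: step for more LDL-C reduction) |

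All six count as modified in 9.7.2 B.

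**2. Effect of pooling on B.2(2).** Let U be the fall after up-titration, D the rise after down-titration, and assume no change for other switches. Then:

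pooled change = p_up x (-U) + p_down x (+D) + p_other x 0

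Illustrative assumptions, not protocol figures, in mg/dL: up-titration 120 to 100 (U = 20), down-titration 20 to 45 (D = 25), other switch 70 to 70.

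| Up / down / other | Mean before | Mean after | Pooled change |
|---|---|---|---|
| 80 / 10 / 10% | 105.0 | 91.5 | -13.5 |
| 60 / 30 / 10% | 85.0 | 80.5 | -4.5 |
| 50 / 40 / 10% | 75.0 | 75.0 | 0.0 |
| 30 / 60 / 10% | 55.0 | 64.0 | +9.0 |
| 10 / 80 / 10% | 35.0 | 53.0 | +18.0 |

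Third row: before 0.5 x 120 + 0.4 x 20 + 0.1 x 70 = 75; after 0.5 x 100 + 0.4 x 45 + 0.1 x 70 = 75. The pooled value always lies between -U and +D. It is exactly zero only when down-titrations make up U/(U + D) of the directional changes, here 20/45 = 0.44. For U and D between 10 and 40 mg/dL that share ranges from 10/50 = 0.20 to 40/50 = 0.80.

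**3. What reporting by regimen settles in 9.7.1 C(1).** Among the approved regimens:
- From 75 mg Q2W, every change is an increase. The reader can infer this.
- From 150 mg Q2W, a change is a decrease or a switch at the same 4-weekly dose. An increase is ruled out, but the two remaining kinds are not separated.
- From 300 mg Q4W, a change is either a decrease or the move that the label describes as a step for more reduction. These are not separated.
- Regimens outside the three approved ones cannot be placed.

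C(3) does not resolve this. A switch from 75 mg Q2W to 300 mg Q4W (+150 mg) and its reverse (-150 mg) are both frequency changes. B.1(2) covers patients very low at any dose, so the regimen split does not help there.

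**4. Numbers available.** Section 9.5.1 assumes about 5% very low among 454 to 574 patients: 0.05 x 454 = 22.7 and 0.05 x 574 = 28.7, so about 23 to 29 patients if all have LDL-C data. One patient is 1/29 = 3.4 to 1/23 = 4.3 percentage points of that group.

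**The case against.** The best defence is that C is already reported by the regimen at which the very low value occurred. Among approved regimens, an increase in 4-weekly dose can appear only in the 75 mg Q2W row, where a reader can recognise it. That stands. A reader might infer that C(1) overstates the protective response throughout; the documents do not support that. The defence does not reach the ambiguities left in step 3, or B.1(2).

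Three other stronger readings also fail:
- That the before/after means do cancel. The protocol gives neither the mix nor the effects, and exact cancellation needs one particular mix.
- That interval-only switches are pooled. No switch among the three regimens changes the interval alone, because the mg per injection changes too. In 9.7.1, frequency change has its own line.
- That the two means in B.2(2) come from different patients. The wording says only that there are two means. It does not require the same patients, but it does not show otherwise.

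It is fair to add that section 9.7.1 asks for quartiles, SD and range, so a mixture would show as spread. But spread in two separate distributions does not tell the reader who moved which way.

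Finally, an SAP could add the split, and nothing in the protocol forbids it. However, section 9.7 presents itself as the specification for the SAP, with differences to be documented, and what it specifies is the pooled measure.

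**Conclusion.** The point holds in a limited form and should be corrected. As written, 9.7.2 B.1 and B.2 pool all regimen modifications. The LDL-C change implied by B.2(2) is attenuated whenever both directions occur and may cancel; by how much cannot be said from the documents. The range of -13.5 to +18.0 mg/dL rests wholly on the assumed effects and mixes above, and on opposite expected LDL-C responses to up- and down-titration.

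In the primary analysis, B.1(2) and C(1)/(3) lack a direction for Praluent that C(4) supplies for other drugs. For C the gap is partial: it concerns the 300 mg Q4W row, switches between 150 mg Q2W and 300 mg Q4W, and off-label regimens. For B.1(2) it is complete. With only about 23 to 29 patients expected to be very low, a few misread changes would matter. None of this bears on the main occurrence proportion, and no dosing rule is judged here.

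**What to change.** - Report 9.7.2 B.1 and B.2, and 9.7.1 B.1(2), C(1) and C(3), by from-to regimen switch.
- Group the switches as up-titration, down-titration or other switch, in line with the label text the protocol quotes. Do not group by total 4-weekly dose alone: that would file 300 mg Q4W to 150 mg Q2W as unchanged, although the quoted label describes it as a step for more LDL-C reduction.
- In 9.7.1 C, show Praluent dose decreased on a separate line from any change.
- Give B.2(2) as the paired within-patient change among patients with both values, and state how many have both.

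The cost is derivation rules and table shells, since section 9.3.3 already collects what is needed. The drawback is sparse cells: present counts per switch, and avoid percentages on very small denominators.
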